6.6.6 Time since first diagnosis

For incomplete information on the date of first diagnosis, time since first diagnosis will be calculated as follows:

- If the year of first diagnosis is unknown, time since first diagnosis will be set to missing.
Note: Every effort should be made to have at least data on year of the first diagnosis populated.
- If day and month of the first diagnosis are unknown, time since first diagnosis will be calculated as if diagnosed on the 30th June of that year.
- If only the day of the first diagnosis is unknown, time since first diagnosis will be calculated as if diagnosed on the 15th of that month.

6.7 BASELINE, TIME WINDOWS AND CALCULATED VISITS

Measurements reported with date and time and taken prior to start of administration of trial treatment will be considered pre-treatment values. Measurements reported with a date only (and no time) and taken on the day of first administration of trial treatment will also be considered pre-treatment values. These pre-treatment values will be assigned to visits according to the nominal visit number as recorded on the eCRF or as provided by the laboratory. For definitions used in Safety analyses, refer to [Section 7.8](#).

Baseline, unless otherwise specified, is defined as the last measurement collected prior to the start of administration of the trial treatment.

Measurements taken after start of administration of trial treatment will be considered either on- or off-treatment values based on the definition in [Section 6.1](#), and will be assigned to visits for statistical analysis, if applicable, as defined below.

Analysis of AE data, concomitant medication or non-drug therapies will not be based on visits. Therefore, no assignment to time windows will be necessary for such data.

For derivation of the last value on treatment, minimum value on treatment, and maximum value in the trial phase, all values from the relevant phase (whether or not collected in any time window; see [Table 6.1: 1](#) for definition of the trial periods/phases) will be considered; these will be derived for analysis of laboratory and vital signs data. For identification of potentially clinically significant abnormal laboratory values, all values (whether or not selected in any time window) before the date of EoS Participation visit will be considered.

A graphical analysis of the ALT and total bilirubin will be performed (so called eDISH plot) based on the available data obtained during the on-treatment period.

All other safety, efficacy and biomarker measurements will be assigned to visits based on extended time windows around the planned visit dates, defined relative to the day of first trial treatment (which is scheduled for Visit V2). These extended time windows are defined in [Table 6.7: 1](#).

Table 6.7: 1 Time windows for assignment of efficacy, safety lab, vital signs, and biomarker measurements to visits for statistical analysis of the double-blind treatment period

Visit number / name	Visit label	Planned day	Time window (Days)				
			Window (per CTP)	Start (per CTP)	End (per CTP)	Start (extended)	End (extended)
V1	Screening	- 28 to -7	n/a			$-\infty$	0
V2	Day 1	Day 1	n/a	1 ^A	1	1 ^A	1
V3	Week 2	Day 15	+/- 3	12	18	2	21
V4	Week 4	Day 29	+/- 3	26	32	22	42
V5	Week 8	Day 57	+/- 3	54	60	43	70
V6	Week 12	Day 85	+/- 3	82	88	71	98
V7	Week 16	Day 113	+/- 3	110	116	99	Week 16 visit date

Days are counted relative to the day of first treatment, which is defined as Day 1.

^A Note that measurements made at Day 1 and assigned to the on-treatment period (because mistakenly made after start of infusion of trial treatment) via assessment on date and time (i.e. safety laboratory) will not be assigned to Day 1. Such data will be listed only.

[Table 6.7:1](#) needs to be taken only when the measurement occurs between randomisation date and primary endpoint visit date (Week 16 visit date). Any unscheduled visits after Week 16 visit date will not be taken into account in [Table 6.7:1](#).

For measurements after the primary endpoint visit date (Week 16 visit date), including unscheduled visits, refer to the [Table 6.7:2](#).

Table 6.7: 2 Time windows for assignment of efficacy, safety lab, vital signs, and biomarker measurements to visits for statistical analysis after Week 16 visit date

Visit number/ name	Visit label	Planned day	Time window (Days)				
			Window (per CTP)	Start (per CTP)	End (per CTP)	Start (extended)	End (extended)
V7.1*	Week 16OL					Week 16 visit date+1	126
V8	Week 20	Day 141	+/- 3	138	144	127	154
V9	Week 24	Day 169	+/- 3	166	172	155	182
V10**	EoS for R	Day 197	+/- 3	194	200	183	210/
						LD+16 weeks/EoS visit date	
V11a***	EoS for NR	Day 228	+/- 3	225	231	211	238/
						LD+16 weeks /EoS visit date	
V11b***	EoS for NR	Day 309	+/- 3	306	312	239	LD+16 weeks /EoS visit date

Days are counted relative to the day of first treatment, which is defined as Day 1.

LD = Last dose of treatment

EoS = End of Study

R = Responder

NR = Non-Responder

* For vital signs, measurements after EASI responder-non-responder assessment are assigned to Week 16 (V7), after first open-label (OL) treatment

** V10 EoS applies to patients who responded at Week 16 (up to LD+16 weeks); Non-responders receive the last dose of the BI655130 at that Week 28 visit (up to day 252)

*** V11a and V11b apply to patients who did not respond at Week 16 and were re-allocated to BI655130 treatment

Repeated and unscheduled efficacy, safety and biomarker measurements will be handled similarly to scheduled measurements and will also be assigned to a time window depending upon the date of measurement.

Only one observation per time window will be selected for statistical analysis at a particular visit – the value which is closest to the protocol planned visit day will be selected. If there are two observations which have the same difference in days to the planned day, the later value will be selected. If there are two observations on the same day, the worst value will be selected.

Assignment of efficacy observations to visits based on time windows will be based on the non-imputed (observed) data.

For visits without an assigned value based on time windows, a value will thereafter be imputed as defined in [Section 6.6](#). Imputation of efficacy endpoints, when applicable, will be performed based on all available observations obtained during the on-treatment period, irrespective of whether the observation was selected in any time window.

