10- One (1) lesional (L) and One (1) non-lesional (NL) biopsy will be collected at V2 (baseline), One (1) lesional (L) biopsy will be collected at V4 (Week 4) and at V7 (Week 16). One (1) optional lesional (L) will be collected at EoS (V10 for Responders or V11 for Non-Responders). Each skin biopsy of 4.5 mm punch (split into half for IHC and RNASeq) should be collected prior to trial drug infusion.

11- Photographs of skin lesions are to precede skin biopsies and study drug administration. Please refer to Section [5.6](#).

12- Skin tape stripping samples will be collected as close as possible to the site of the skin biopsy and at the same timepoint. Skin tape stripping samples must be taken before biopsies are taken and before trial drug infusion. One (1) L and one (1) NL at V2; one (1) L at V4 (Week 4) and V7 (Week 16); and one (1) optional lesional (L) at EoS(V10 for Responders or V11 for Non-Responders).

13- pre dose PK and ADA and Nab samples will be collected within 2 hour period prior to infusion. In addition, all biomarkers samples will be collected prior to trial drug infusion. Please refer to Section [5.3](#).

14- Microbiome samples must be taken before biopsies are taken and before trial drug infusion.

15- Deoxyribonucleic acid (DNA) banking sample is optional. Participating patients are required to give informed consent specifically for this banking. Blood sample will be collected in a PAX-gene Blood DNA tube at day 1 (Visit 2). If not possible at Visit 2, this sample may also be collected during a later visit. The DNA banking sample must be collected prior to infusion of the trial drug infusion.

16- At V7 (Week 16) all patients will be evaluated with the EASI score. Non-responders will be re-allocated to receive BI open label trial drug from V7 (Week 16) onward until V10 (Week 28). Responders will be re-assigned to no treatment from V7 (Week 16) onward until V10 (Week 28) but will be expected to come to all visits.

Proprietary confidential information © 2020 Boehringer Ingelheim International GmbH or one or more of its affiliated companies

17- All assessments must be done prior to trial drug infusion. The questionnaires completed by patients should be done first before the investigator assessments. Please refer to Section [6.2](#).

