7.3 PLANNED ANALYSES

The efficacy analyses will be performed for the Full Analysis Set (FAS), which is based on the intent-to-treat principle, and comprises all participants who were randomised, received at least one dose during the trial, and had a baseline measurement for the primary endpoint. Efficacy analyses will be based on the planned treatment (i.e., the treatment assigned at randomisation). Safety analyses on patients who were randomised, and received at least one dose during the trial will be based on the actual treatment received at the randomisation visit; this set of patients is called the Safety Analysis Set (SAF). All efficacy analyses will be conducted on the FAS. All safety analyses will be conducted on the SAF. With regard to efficacy and safety endpoints, “baseline” refers to the measurement recorded at randomisation (Visit 2), if data at Visit 2 is missing, then data from Visit 1 will be considered baseline.

Important deviations of the protocol will include key inclusion and exclusion deviations, incorrect medications taken, compliance with study medication, concomitant use of restricted medications, and any other deviations of the protocol deemed important by the study team. All decisions concerning important protocol deviations will be made prior to un-blinding of the database for the primary week 16 analysis. This is an exploratory trial and sensitivity analyses may need to be done to investigate the effects of potential confounding factors.

Standard statistical parameters (number of non-missing values, mean, standard deviation (SD), median, quartiles, minimum, and maximum) or frequency tables (including patient frequencies and percentages) will be calculated where appropriate.

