 - **"Speso 600 mg IV q4w"** (i.e., patients randomised to BI 655130 in the double-blind treatment period and who did not receive an open-label BI 655130 treatment starting from Week 16 (V7))
 - **"Total"** (i.e., patients randomised either to Placebo or BI 655130 in the double-blind treatment period and who did not receive an open-label BI 655130 treatment starting from Week 16 (V7))
- **"Open-label treatment: Speso 600 mg IV q4w"**
 - **"Placebo"** (i.e., patients randomised to Placebo in the double-blind treatment period and received an open-label BI 655130 treatment starting from Week 16 (V7))
 - **"Speso 600 mg IV q4w"** (i.e., patients randomised to BI 655130 in the double-blind treatment period and received an open-label BI 655130 treatment starting from Week 16 (V7))
 - **"Total"** (i.e., patients randomised either to Placebo or BI 655130 in the double-blind treatment period and received an open-label BI 655130 treatment starting from Week 16 (V7))

Treatment groups for the safety analysis for the whole trial will be labelled as follows:

- **"Speso 600 mg IV q4w"** (i.e., patients randomised to BI 655130 600 mg)
- **"Placebo"** (i.e., patients randomised to Placebo)
- **"Total Speso 600 mg IV q4w OL"** (i.e., patients randomised either to Placebo or BI 655130 600mg and assigned to BI 655130 600 mg open-label treatment at Week 16)

More details on the technical implementation of these analyses are provided in the ADS Plan of this TSAP.

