7.8.2 Laboratory data

The analyses of laboratory data will be descriptive in nature and will be based on BI standards (8). Note that data from the central Laboratory will be used for all displays described below, unless otherwise specified.

The analyses of safety laboratory parameters will be performed for the double-blind period and re-allocation period separately.

For continuous safety laboratory parameters, normalized values will be derived.

Normalisation means transformation to a standard unit and to a standard reference range. The process of normalisation, handling of repeat values at the same visit for by-visit displays, as well as standard analyses for safety laboratory data are described in the BI guidance for the “Handling, Display and Analysis of Laboratory Data” (8). All analyses considering multiple times of the ULN (as described below) will be based on standardized and not normalized values. For continuous safety laboratory parameters, differences to baseline will be calculated.

Only patients with at least one available post-baseline value will be included in the analysis of an individual laboratory parameter. All individual laboratory data will be listed. Values outside the reference range will be flagged.

Descriptive statistics of laboratory values over time and for the difference from baseline (see Section 6.7) will be based upon normalised values and provided by visit, including summaries of the last value on treatment, the minimum value on treatment and maximum value in the respective period (double-blind or re-allocation).

Laboratory values will be compared to their reference ranges; shift tables will be provided for the number of patients with a specific RCTC grade at baseline versus the grade at the last measurement on treatment, as well as the worst grade on treatment. These analyses will be based on standardized laboratory values.

In addition, box and whiskers plots will be presented for the laboratory parameters.

Potentially clinically significant abnormalities will be identified based on BI standard rules which are based on normalized converted lab values, i.e. using SI units. These rules will be listed in the SDL appendix of the CTR. Frequency tables will summarize the number of patients with potentially clinically significant abnormalities. Patients having an abnormal lab value at baseline will be presented separately. A separate listing will present potentially clinically significant abnormal lab values.

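### For former placebo patients, open-label laboratory and vital-sign changes are measured from before the first blinded infusion, so placebo-period and on-drug change are combined in one pooled column

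*SAP*

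**What the plan says.** SAP 6.7 gives one general definition: "Baseline, unless otherwise specified, is defined as the last measurement collected prior to the start of administration of the trial treatment". The same section ties trial treatment to the first blinded infusion, since the visit windows are "defined relative to the day of first trial treatment (which is scheduled for Visit V2"). Protocol 7.3 agrees. For efficacy and safety endpoints, baseline "refers to the measurement recorded at randomisation (Visit 2"), with Visit 1 as the fallback if Visit 2 is missing.

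SAP 7.8.2 then splits the laboratory analysis by period: "The analyses of safety laboratory parameters will be performed for the double-blind period and re-allocation period separately". It takes its baseline from the general rule: "Descriptive statistics of laboratory values over time and for the difference from baseline (see Section 6.7) will be based upon normalised values". It also plans shift tables of RCTC grade at baseline against the last and the worst grade on treatment. For potentially clinically significant values it adds: "Patients having an abnormal lab value at baseline will be presented separately". SAP 7.8.3 treats vital signs in the same way, by period and with reference to Section 6.7.

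For safety over the whole trial, SAP 6.1 provides a single open-label group: "patients randomised either to Placebo or BI 655130 600mg and assigned to BI 655130 600 mg open-label treatment at Week 16". For efficacy after Week 16, the same section shows each randomised arm and the total.

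**The concern.** A patient randomised to placebo who is a non-responder at Week 16 receives BI 655130 for the first time then. The defined baseline for that patient lies 16 weeks before first exposure. A laboratory or vital-sign change that arose on placebo and persisted is therefore displayed as a change under open-label BI 655130. The reverse can also happen: an abnormality present at Visit 2 that resolved by Week 16 and recurred on drug shows as no shift.

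Safety and tolerability are part of the primary objective, and Protocol 2.1.1 says they can only be analysed descriptively. The tables are therefore the evidence, and former placebo patients are the only ones whose first exposure falls in the open-label period. The SAP already separates the two exposures for adverse events. In Table 6.1: 2, events in placebo non-responders before the Week 16 visit date go to placebo, and later ones go to open-label treatment. Laboratory and vital-sign changes have no matching rule.

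**Working it through.** The plan states no figure on this point, so there is none to reproduce. The check is of the text, followed by an illustration of size.

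**1. Is another baseline given?**
- SAP 6.7 allows exceptions where otherwise specified and sends the reader to Section 7.8 for safety definitions.
- SAP 7.8, 7.8.2 and 7.8.3 define no other baseline. The last two point back to 6.7.
- Protocol 7.3 names Visit 2 for safety as well as efficacy.

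The cross-references are circular, and every visible rule leads to the value before the first blinded infusion.

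**2. What the tables then measure.** Write Y0 for the value before the first blinded infusion, Y16 for the value before the Week 16 infusion, and Y for a later open-label value.

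Reported change = Y − Y0 = (Y16 − Y0) + (Y − Y16)

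- Randomised to BI 655130: both terms are on drug, so Y0 is the right reference.
- Randomised to placebo: the first term is on placebo and only the second is on drug. Both appear under open-label BI 655130.

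**3. The shift table, for a placebo patient.**
- Grade 0 at Visit 2, grade 1 at Week 16, grade 1 on drug: reported as a shift from 0 to 1 in the open-label period, although nothing changed on drug.
- Grade 1 at Visit 2, grade 0 at Week 16, grade 1 on drug: reported as no shift, although the grade rose on drug. In the table of potentially significant values, a patient abnormal at Visit 2 is likewise placed in the separate abnormal-at-baseline group.

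Only changes still present after Week 16 carry over. One that arose on placebo and resolved before then does not.

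**4. Share of the pooled column.** Planned arm sizes are 30 active and 15 placebo (Protocol synopsis). Let rp and ra be the Week 16 EASI75 rates on placebo and active. These are assumptions, because the documents give none. Dropout is ignored.

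Share of former placebo patients = 15(1 − rp) / [15(1 − rp) + 30(1 − ra)]

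| rp | ra | Former placebo | Former active | Share |
|---|---|---|---|---|
| 0 | 0 | 15 | 30 | 33% |
| 0.1 | 0.4 | 13.5 | 18 | 43% |
| 0.3 | 0 | 10.5 | 30 | 26% |
| 0 | 0.6 | 15 | 12 | 56% |

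The share falls as rp rises and rises with ra, so the last two rows are the extremes for rp of 0-30% and ra of 0-60%.

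**5. Effect on a mean.** If former placebo patients carry a persisting mean change D from the placebo period and the drug does nothing, the pooled open-label mean change contains share × D. For D = 1 unit this is about 0.26 to 0.56 units.

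**6. Are the values for a better baseline collected?** The Flow Chart schedules safety laboratory tests and vital signs at Visit 7. Protocol 6.1 places measurements at dosing visits before drug administration, and Protocol 5.2.2 requires pre-dose vital signs. Flow Chart footnote 17 ("All assessments must be done prior to trial drug infusion") is weaker support, because it is attached to the efficacy and DLQI rows and the Visit 7 header, not to the laboratory or vital-sign rows.

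**The case against.** The strongest reply is that little of clinical weight is misattributed. Under SAP 7.8.2 and 7.8.3, findings judged clinically relevant are analysed as adverse events, and Table 6.1: 2 assigns those arising before Week 16 in placebo non-responders to placebo. Values are also summarised by visit, all individual laboratory data are listed with out-of-range values flagged, double-blind tables are separate, and no safety hypothesis is tested. The liver-enzyme counts by multiples of ULN use no baseline. All of this stands, and it confines the problem to the change and shift tables and the abnormal-at-baseline split.

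A second reply is that Visit 2 is the protocol's own safety baseline and keeps comparability with the double-blind tables. That is true. It means the fix departs from Protocol 7.3 and must be recorded, and that splitting the column by arm is useful in its own right.

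Four stronger readings are tempting and not supported:
- A reader might infer that open-label safety attribution is wrong in general. The adverse-event rule shows otherwise.
- A reader might infer that no other baseline applies anywhere. The definition allows exceptions, some SAP text is redacted, and neither the ADS Plan nor the sponsor's laboratory guidance is supplied. Only the visible text can be judged.
- A reader might infer that patients abnormal at baseline are dropped. They are presented separately, and potentially significant values are also listed.
- A reader might want a count of patients misreported. That needs a rate of persisting shifts on placebo, which the documents do not give.

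**Conclusion.** The point holds as a limited attribution problem. Followed as written, the visible SAP measures open-label laboratory and vital-sign change in former placebo patients from a value 16 weeks before their first BI 655130 dose, and the only open-label safety column pools them with patients already exposed. The distortion can run in either direction. Its size depends on how much change persists from the placebo period and on the share of former placebo patients: 33% with no responders, about 26% to 56% over the assumed rates, with 30 and 15 randomised and no dropout.

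It does not touch the efficacy analysis, the adverse-event attribution or the double-blind safety tables. It is worth correcting before the final analysis because the tables are descriptive safety evidence and the remedy is cheap.

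**What to change.** In SAP 6.7 and 7.8, for re-allocation-period laboratory and vital-sign summaries in patients receiving open-label BI 655130, define baseline as the last value before the first BI 655130 dose:
- randomised to BI 655130: the value before the first infusion, as now;
- randomised to placebo: the Week 16 value before the infusion.

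State that post-infusion vital signs at Week 16 are excluded from this selection. Otherwise the SAP 6.7 rule of choosing the worst of two same-day values could pick one taken after dosing.

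Show columns by randomised arm beside the open-label total, as SAP 6.1 already does for efficacy. Leave the baseline for efficacy and for the double-blind period unchanged. Record the departure from Protocol 7.3 in SAP section 4, which now reads NA.

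The cost is SAP wording, a second baseline flag and extra columns; no new data are needed. The drawback is two baselines to explain in the report, and an open-label total whose reference point differs by randomised arm. The split columns make that visible.

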18- For Responders (R) the EoS visit must be completed 16 weeks after last treatment, which is at the latest at Week 28 (V10). Responders (R) may complete EOS at any point after V7 (Week 16) if the patient drops to an EASI 50 score prior to the planned EOS. For Non Responder (NR) patients who have achieved EASI 50 and plan to participate in the extension trial, the EoS visit will be completed no earlier than Week 32. Non Responder patients not participating in the extension trial will complete a V11/FU1 visit between Week 32-44. If a patient should discontinue treatment prematurely every effort should be made to keep the patient in the trial and complete all of the remaining study visits or at a minimum an early EoS visit 16 weeks after last treatment.

[figure not shown]
19- At V1 (Screening) BSA will be assessed for eligibility. From V2 (baseline) onward BSA will be completed as part of SCORAD assessment.

20- Only Non-Responders not participating in the open label extension trial must complete an End of Study Safety Phone Call. V11 and End of Study Safety Phone call can occur on the same day only if the Residual Effect Period (16 weeks after last trial drug infusion) has been reached (WK44). The phone call cannot be performed before the V11.

21- Patients will be asked about their pregnancy status at the End of Study Safety Phone Call.

22- For Non-Responders participating in the open label extension trial, End of Study completion IRT call is registered at V11 as the End of Study Safety Phone Call is not required. For Non-Responders not participating in the open label extension trial, End of Study completion IRT call is registered only at End of Study Safety Phone Call (WK44). V11 is not registered in IRT.

TABLE OF CONTENTS

TITLE PAGE	1
CLINICAL TRIAL PROTOCOL SYNOPSIS	2
FLOW CHART	6
TABLE OF CONTENTS	10
ABBREVIATIONS	13
1. INTRODUCTION.....	16
1.1 MEDICAL BACKGROUND	16
1.2 DRUG PROFILE	17
1.2.1 Mode of Action	17
1.2.2 Nonclinical pharmacology.....	17
1.2.3 Clinical experience	18
1.3 RATIONALE FOR PERFORMING THE TRIAL	20
1.4 BENEFIT - RISK ASSESSMENT.....	20
2. TRIAL OBJECTIVES AND ENDPOINTS.....	22
2.1 MAIN OBJECTIVES, PRIMARY AND SECONDARY ENDPOINTS.....	22
2.1.1 Main objectives.....	22
2.1.2 Primary endpoint	22
2.1.3 Secondary endpoint(s)	22
	
3. DESCRIPTION OF DESIGN AND TRIAL POPULATION	24
3.1 OVERALL TRIAL DESIGN AND PLAN	24
3.2 DISCUSSION OF TRIAL DESIGN, INCLUDING THE CHOICE OF CONTROL GROUP(S)	25
3.3 SELECTION OF TRIAL POPULATION	25

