5. ENDPOINTS

For all endpoints and unless explicitly specified otherwise, Week numbers refer to specific Visit numbers using extended time windows as defined in [Table 6.7: 1](#) and [Table 6.7:2](#).

For all endpoints and unless explicitly specified otherwise, End-of-Study visit refers to V10 (Week 28) for Responders and V11 (Week 44) for Non-Responders, using extended time windows as defined in [Table 6.7: 1](#) and [Table 6.7:2](#).

Responders are defined as patients who attain at least 75% reduction in Eczema Area and Severity Index (EASI) score compared to baseline at Week 16. Non-Responders are defined as patients who do not achieve at least 75% improvement from baseline in EASI score at Week 16.

For handling of missing data and corresponding sensitivity analyses, see [Section 6.6](#).

Definition of baseline is provided in [Section 6.7](#).

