6. GENERAL ANALYSIS DEFINITIONS

6.1 TREATMENTS

For basic study information on the treatment to be administered, assignment to treatment, and selection of dose, cf. Section 4 of the CTP.

In the blinded treatment phase, all patients will receive either intravenous doses of 600mg of BI 655130 solution for infusion (at weeks 0, 4, 8, and 12), or Placebo.

At Week 16, all patients will be evaluated with the EASI Score. Non-responders (EASI < 75) will be re-allocated to receive BI open label trial drug from Week 16 through Week 28; they will be followed until Week 44. Responders (EASI >= 75) will be re-assigned to receive no further trial treatment but will be expected to come to all visits up to Week 28, when EOS visit is planned.

The following trial periods/phases are defined:

Table 6.1: Flow chart of trial period/phases

Trial phase	Description	Start (included)	End (excluded)
Screening phase	Screening	Date of informed consent	Date of start of first infusion of study drug (day 1).
Blinded Treatment phase	Randomised On-treatment period	Date of start of infusion of first study drug (Day 1)	Week 16 visit date + 1 day
Open label Treatment phase ¹	Re-allocation period (Either open label BI655130 or No treatment)	Week 16 visit date + 1 day	Date of EoS Participation visit + 1 day

Dates are defined individually per patient. If more than one date is associated with a specific visit, measurements associated with a specific date are assigned to a study analysis phase according to the rules specified in the table. An analysis phase will not extend beyond the start date of the following phase.

¹ Non-responders (i.e. EASI<75) at Week 16 will be re-allocated to BI655130 600mg IV open label and will continue in the trial until Week 44. Responders (EASI>=75) at Week 16 will be re-allocated to no treatment and will be observed until Week 28 or the day when they return to a 50% reduction in EASI score (EASI50) and start the treatment in the extension trial.

Patients who discontinue the treatment but will continue on trial visits will be included in analyses with the available data. For patients who discontinue trial prematurely only available data will be used in the analyses.

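### The SAP 6.7 search for potentially clinically significant laboratory values stops the day before end of study, so non-responders infused at V10 whose EoS date is V11 have no scheduled sample after the last infusion screened

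*SAP*

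**What the plan says.** SAP 6.7 gives the date range for the PCSA search: "all values (whether or not selected in any time window) before the date of EoS Participation visit will be considered". SAP 7.8.2 uses the search for a frequency table of patients and a separate listing. It gives no other date range and refers to the sponsor's standard rules for the abnormality criteria.

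Two other places in the SAP treat the EoS day differently. Table 6.1: 1, whose end column is marked as excluded, closes the last phase at "Date of EoS Participation visit + 1 day", so the EoS day lies inside the phase. Table 6.7: 2 allows the V10 and V11 windows for safety laboratory data to extend to the EoS visit date, and its footnote says that "V11a and V11b apply to patients who did not respond at Week 16 and were re-allocated to BI655130 treatment".

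The documents do not agree on which date is a non-responder's end of study:

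- SAP 5 states that "End-of-Study visit refers to V10 (Week 28) for Responders and V11 (Week 44) for Non-Responders".
- Protocol Flow Chart footnote 22 agrees for one group: "For Non-Responders participating in the open label extension trial, End of Study completion IRT call is registered at V11". For this group footnote 18 adds that "the EoS visit will be completed no earlier than Week 32".
- For non-responders who do not enter the extension, footnote 22 says: "End of Study completion IRT call is registered only at End of Study Safety Phone Call (WK44). V11 is not registered in IRT".

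The term used in the PCSA rule, EoS Participation visit, is not defined.

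**The concern.** The Flow Chart schedules safety laboratory tests at V10 and V11. Non-responders receive their last infusion at V10 (footnote 2), and Protocol 6.1 has assessments at dosing visits completed before the infusion. Any laboratory change that follows the last infusion can therefore first be seen, at a scheduled visit, at V11. If V11 is also the EoS date, a programmer who follows the sentence literally leaves that sample out of the PCSA table and listing.

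Protocol 2.1.1 calls safety and tolerability the main objective and says that it can only be analysed descriptively, so these two outputs are part of how that objective is reported. SAP 4 declares no change to the planned analysis, which suggests that the cut-off is not a deliberate departure from it.

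**Working it through.** The plan states no figure to reproduce. The check applies the date rule to the planned laboratory days.

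**Inputs.** Planned days from the Flow Chart and SAP Tables 6.7: 1 and 6.7: 2: V3 = 15, V4 = 29, V5 = 57, V6 = 85, V7 = 113, V8 = 141, V9 = 169, V10 = 197, V11 = 228 to 309. Last infusion for a fully dosed non-responder: V10, after the V10 sample. Last infusion for a responder: V6. The earliest V11 under footnote 18 is Week 32, which is 32 × 7 + 1 = Day 225.

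**Rules compared.** As written: sample day < EoS day. Table 6.1: 1 boundary: sample day < EoS day + 1.

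**Scheduled samples after the last infusion:**

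| Patient | Samples after last infusion | Screened as written | Screened to EoS day + 1 |
|---|---|---|---|
| Non-responder infused at V10, EoS = V11 (Day 225, 228 or 309) | V11 | 0 of 1 | 1 of 1 |
| Non-responder infused at V10, outside extension, V11 on Day 228, EoS read as the Day 309 call | V11 | 1 of 1 | 1 of 1 |
| Same, V11 on the day of the call (Day 309) | V11 | 0 of 1 | 1 of 1 |
| Non-responder who stops after the V8 infusion and attends to V11 on Day 228 | V9, V10, V11 | 2 of 3 | 3 of 3 |
| Responder, EoS = V10 | V7, V8, V9, V10 | 3 of 4 | 4 of 4 |

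The third row can occur because footnote 20 lets the visit and the call coincide: "V11 and End of Study Safety Phone call can occur on the same day only if the Residual Effect Period" of 16 weeks has been reached.

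**Share of all post-baseline samples.** A non-responder with EoS at V11 has V3 to V11 = 9 scheduled samples, of which 8 are screened. In the re-allocation phase there are V8 to V11 = 4, of which 3 are screened. A responder with EoS at V10 has V3 to V10 = 8, of which 7 pass the cut-off.

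**When the omitted V11 sample is taken.** By planned days it falls 228 − 197 = 31 to 309 − 197 = 112 days after the last infusion, and 225 − 197 = 28 days at the earliest Week 32 date. Protocol 7.3.4 sets the residual effect period at 16 weeks (112 days), and 197 + 112 = 309. At its planned days, V11 therefore lies within the period that the protocol assigns to treatment for adverse events.

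**The case against.** The strongest reply is that this is loose drafting. The same sentence has no lower limit, so read literally it would also take in screening and baseline values, which SAP 7.8.2 plainly handles separately. The sentence just before it relies on the Table 6.1: 1 phases, which keep the EoS day. The sponsor's standard laboratory rules and the analysis dataset plan are not among the documents, and either might settle the range. All of this is fair, and the wording may well be a slip. But the sentence is the only visible date range for the PCSA outputs, and it conflicts with the SAP's own tables, so correcting it is still warranted.

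A reader might also infer that every non-responder goes unscreened after the last infusion. The documents do not support that. Patients who stopped dosing before V10 but kept attending visits have other samples after their last infusion that are screened. For those outside the extension, an earlier V11 is kept if the EoS date means the Week 44 call.

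Nor can one infer that late abnormalities vanish from the report. On the SAP's text, V11 values still enter the by-visit summaries, the last, minimum and maximum values, the RCTC shift tables and the liver threshold tables. All individual values are listed with out-of-range flags, and findings that the investigator judges clinically relevant are reported as adverse events.

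**Conclusion.** Wrong as written, and minor. SAP 6.7 and Table 6.1: 1 disagree on whether the EoS day counts, and the literal PCSA rule excludes it.

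The firm case is the non-responder infused at V10 who enters the extension: V11 is the EoS visit and 0 of 1 scheduled samples after the last infusion is screened, instead of 1 of 1. Under the SAP 5 definition the same applies to every non-responder infused at V10. For those outside the extension it otherwise depends on the undefined term. For responders with EoS at V10, the V10 sample fails the cut-off, but V7 to V9 pass.

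The conclusion assumes that the sentence is programmed literally and that no unseen standard overrides it. The documents do not say how many patients enter the extension, so the number affected cannot be given. Only the PCSA table and listing change; no endpoint, test or other laboratory output does.

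**What to change.** In SAP 6.7, set the PCSA range to post-baseline values up to and including the date of the EoS Participation visit, matching Table 6.1: 1. Define that term for responders, for non-responders entering the extension and for non-responders with a safety phone call, so that the V11 laboratory sample is always included for non-responders.

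The cost is one changed phrase and one definition. No new data, visits or tables are needed.
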